### **5.2.2 Safety Precaution Information**

A leaflet with safety precautions for using the Viaskin® patch and instructions to follow in case of any safety issue will be given to each subject. This safety leaflet will specify at least the following information:

1. Instructions and procedures to apply the patch safely and correctly in the back of the subject;
2. Necessity to call the investigative site staff in case of intense or severe local reactions lasting for more than 1 day or any unexpected reactions during the treatment period, in particular any appearance of vesicles/blisters under the patch or close to the area of patch application and a recommendation to take photos of the site of application to document such a situation;
3. Necessity to call the investigative site staff in case of occurrence of chicken pox or measles. At the same time, interruption of patch application until recovery;
4. In case of active eczema extending on the back of the child: stop applying the patch until recovery from the active eczema on the back;
5. Anaphylaxis Emergency Action Plan in case of a suspected anaphylactic reaction and how to administer the epinephrine auto-injector to rapidly treat the reaction;
6. Subject stopping rules (subject are consequently withdrawn):
  - a. Severe "maculo-papular rash" or severe "dermatitis" at sites of patch application not controlled by topical corticosteroids,
  - b. Severe anaphylaxis related to Viaskin® Peanut 250 µg patch application confirmed by an expedited safety review.
  - c. More than 1 epinephrine injection in relation to Viaskin® Peanut 250 µg patch application (and not occurring during DBPCFC).

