### 4.3 Patient Withdrawal and Replacement

#### 4.3.1 *Criteria for Withdrawal from Study Treatment and Study*

Subjects may withdraw from the study including follow-up at any time without penalty and for any reason without prejudice to their future medical care.

Subjects must be withdrawn from the **study treatment** under the following circumstances:

- Pregnancy (see [Section 6.2.1.7](#));
- Severe “maculo-papular rash” or severe “dermatitis” failed to be controlled by adequate corrective treatments (including topical corticosteroids) and in spite of several study treatment interruptions;
- Severe anaphylaxis (or stage 3 anaphylaxis) (see [APPENDIX 5](#)) related to Viaskin® Peanut 250 µg patch application;
- More than 1 epinephrine injection for an AE related to Viaskin® Peanut 250 µg patch application (and not occurring during the DBPCFC).

If subjects are to withdraw due to pregnancy, the procedures that should be followed are described in [Section 6.2.1.7](#).

Subjects may be required to withdraw from the **study treatment or study** after discussion with the Sponsor and/or Investigator for the following reasons:

- AE(s);
- At the discretion of the Investigator, if she/he decides that it is in the subject’s best interest to be withdrawn from the study;
- The subject is unwilling to continue in the study (consent withdrawal);
- Lack of compliance with protocol requirements and procedures;
- The Sponsor, Regulatory Authorities, or Independent Ethics Committees (IECs)/Institutional Review Boards (IRBs) for any reason, stop the study;

- The subject fails to return to the clinic for scheduled visits and does not respond to telephone or written attempts at contact (lost to follow-up);
- Premature termination of the entire study as described in [Section 9.11](#).

In all cases, the primary reason for withdrawal, must be recorded in the e-CRF.

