#### **4.3.2 Study Stopping Rules**

Study enrollment will be suspended pending an expedited safety review by the independent DSMB if any of the following occur:

1. Any death related to Viaskin® patch dosing;
2. More than one case of severe anaphylaxis (or stage 3 anaphylaxis) (see [APPENDIX 5](#)) related to Viaskin® Peanut 250 µg patch application (not occurring during the DBPCFC);
3. More than 3 subjects requiring more than 1 injection of epinephrine for an AE related to the Viaskin® Peanut 250 µg patch application (and not occurring during the DBPCFC).

Upon safety review, 1 of the following outcomes will be determined:

- Accrual to the study may continue without modification;
- Accrual to the study may continue with modifications as prescribed by the DSMB;
- Accrual to the study should be discontinued.

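### Leaflet item 6b (Protocol 5.2.2) makes the subject stopping rule for patch-related severe anaphylaxis depend on an expedited review that Protocol 4.3.1 does not require

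*Protocol*

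**What the plan says.** Protocol 4.3.1 lists the circumstances in which a child must be taken off study treatment. One begins "Severe anaphylaxis (or stage 3 anaphylaxis" and requires only that the event be related to the patch. Another is "More than 1 epinephrine injection for an AE related to" the patch, outside the food challenge. A separate list in 4.3.1 permits withdrawal "At the discretion of the Investigator, if she/he decides that it is in the" child's best interest.

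Protocol 5.2.2 gives the least that the leaflet must contain. Under subject stopping rules, item 6b covers severe anaphylaxis related to Viaskin Peanut 250 µg "patch application confirmed by an expedited safety review". Item 6c repeats the rule on more than 1 epinephrine injection. Under 7.2.4 the leaflet is handed out at Visit 4.

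Protocol 4.3.2 describes an expedited review in these terms: "Study enrollment will be suspended pending an expedited safety review by the independent DSMB if any of the following occur". It lists three triggers and three possible outcomes.

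Protocol 5.2.1 deals with adjusting patch wear. After any suspected systemic reaction to the patch, the patch is removed, treatment may be given, and the next patch goes on the following day. No exception is stated for stage 3 anaphylaxis.

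**The concern.** The protocol gives two versions of one subject-level stopping rule. The version for investigators is unconditional. The version for families waits for confirmation, and 5.2.2 does not say who confirms, how quickly, or what the family does meanwhile.

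Appendix 5 defines stage 3 by features such as cyanosis or SpO2 of 92% or less, hypotension, collapse or loss of consciousness. The subjects are children aged 4 through 11 who are treated at home every day. After such an event the stopping instruction should be the same wherever it appears. The general next-day reapplication instruction in 5.2.1 adds to the ambiguity because it carries no stage 3 exception.

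**Working it through.** No arithmetic beyond counting applies, and the plan states no figure to reproduce. The check takes one case, a first, non-fatal, patch-related stage 3 anaphylaxis, and reads it against each rule.

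**Step 1. Does 4.3.2 call a review for this case?**

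| Trigger in 4.3.2 | Needed | This case contributes | Met by this case alone? |
|---|---|---|---|
| "Any death related to Viaskin" patch dosing | 1 death | 0 | No |
| "More than one case of severe anaphylaxis (or stage 3 anaphylaxis") | at least 2 cases | 1 | No |
| More than 3 subjects, each needing more than 1 epinephrine injection | at least 4 subjects | 0 or 1 | No |

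The third trigger is a study-wide count. This child could complete it if 3 others already qualified (3 + 1 = 4), but only after more than 1 injection, in which case both lists withdraw the child anyway. With 0 or 1 injection the child adds 0 to that count.

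**Step 2. Would that review confirm an individual case?** The three listed outcomes are to continue accrual, to continue it with modifications the DSMB prescribes, or to discontinue it. The second is open-ended, but none is expressed as confirming one child's event. From the second case onward the second trigger is met and a review does take place, with the same listed outcomes.

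**Step 3. Is another review described?** Section 9.9 allows ad hoc DSMB review when the chair thinks it necessary or the sponsor asks. It does not call this expedited or tie it to a first case. In 5.4 and 6.2.1.3.1 the word expedited concerns reporting, not review. The SAP section on the DSMB (4.9.11) adds nothing on this point.

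**Step 4. Where do the two lists differ?**

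| Epinephrine injections given | 4.3.1 | 5.2.2, item 6 |
|---|---|---|
| 0 or 1 | Withdraw (anaphylaxis rule) | 6b applies only if a review confirms; 6c not met |
| More than 1 | Withdraw (anaphylaxis and epinephrine rules) | Withdraw (6c) |

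The mismatch is therefore confined to a related stage 3 case treated with no more than 1 injection.

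**Step 5. How often might this arise?** The documents give no usable rate. VIPES had no SAE related to Viaskin Peanut, and Protocol 1.1.1.2.6 reports that no children withdrew because of AEs. ARACHILD, at 100 µg, had 1 anaphylactic reaction among 4 SAEs judged possibly related. It followed a food exposure, and no stage is given. Such events look rare, and nothing firmer can be said.

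**The case against.** The strongest reply is that 4.3.1 is the operative rule and is mandatory. Item 6b names one circumstance that leads to withdrawal. It does not say that a child stays on the patch pending review, so a site can withdraw under 4.3.1 without breaching 6b. The leaflet itself is not among the documents, so its final wording is unknown. Families are told to call the site about any unexpected reaction (5.2.2, item 2) and receive an emergency action plan (item 5). SAEs are reported within 24 hours (6.2.1.5), and the investigator may withdraw a child at discretion. All of this stands and lowers the practical risk. It does not explain why the family version carries a condition that the investigator version lacks.

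Three stronger readings are tempting, and the documents do not support them.

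- A reader might infer that 5.2.1 directs re-exposure the day after collapse. That text belongs to a section on shortening wear time, and its named treatments are antihistamines and corticosteroids, without epinephrine. Milder reactions were probably meant, and 4.3.1 supplies the mandatory stop. The change to 5.2.1 is a clarification.
- A reader might infer that no review route exists at all. Section 9.9 leaves a discretionary one, lets the DSMB recommend corrective action in subjects' interest, and refers its operations to a Charter we cannot see. The supportable statement is that the protocol text describes no expedited review for a first non-fatal case.
- A reader might infer that leaflet item 6a contradicts the skin rule in 4.3.1. Section 4.3.1 requires that the reaction "failed to be controlled by adequate corrective treatments (including topical corticosteroids) and in spite of several study treatment interruptions". It does not state a site. Item 6a refers to patch sites and does not mention interruptions or treatments other than topical corticosteroids. These are omissions of a kind a short summary may make, not opposing rules.

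**Conclusion.** The point holds as a wording conflict. Item 6b adds a confirmation step that 4.3.1 does not contain, and the protocol text describes no expedited review that a first non-fatal case would set in motion by itself. Section 4.3.1 would probably govern at sites, although no order of precedence is stated. The conflict therefore lies mainly in what families are told.

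Its reach is narrow: related stage 3 events treated with 0 or 1 epinephrine injection. The documents do not show that any child would be kept on treatment after such an event, and they support no probability.

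The primary ITT analysis is unaffected. SAP Appendix 1 treats a subject who met withdrawal criteria but was not withdrawn as a major deviation, with possible exclusion from the PP population, so an unambiguous rule also helps that classification.

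The conclusion assumes that the issued leaflet follows the content specified in 5.2.2 and that the unseen Charter does not define an expedited review of single cases. Even if the Charter does, 6b and 4.3.1 would still differ. The change is worth making because it concerns a life-threatening event in children and costs little.

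**What to change.** Delete the confirmation clause from item 6b, so that it ends at patch application and matches 4.3.1. If the sponsor wants a case review, say that it follows the stop and is not a condition for it.

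Add to 5.2.1: *Next-day reapplication does not apply after severe (stage 3) anaphylaxis related to the patch; study treatment is stopped as in Section 4.3.1.*

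The cost is wording in two protocol sections, handled as an amendment under 9.8, and a reissued leaflet if the printed one carries the clause. Sample size, endpoints and analyses do not change.

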### ***5.2.1 Adjustment of Viaskin® Patch Application in Case of Local or Systemic Reactions***

When subjects are unable to apply the Viaskin® patch for the recommended durations as described above because of local intense or severe reactions, under or adjacent to the patch site, the patch should be removed immediately, the site of application wiped with a moist disposable tissue and a topical corticosteroid medication might be topically applied to treat the reaction. The parents/guardians should take a photo of the back of the subject to document how intense and extended the local reactions are. In the specific case of local intense or severe reactions, it is mandatory that the next Viaskin® patch is applied only the next day on the next zone; no other Viaskin® patch must be applied the same day. In case of re-appearance of the local intense or severe reactions after application of the next patch the following day, the patch must again be removed. The next Viaskin® patch should be applied only the next day on the next zone. And the same process is repeated every day after patch application in case of local intense or severe reactions.

As a consequence, the daily duration of Viaskin® patch application should be adjusted/reduced as necessary, and subjects may need more than the 14 days previously described before they can apply and tolerate the Viaskin® patch for the full 24 hours daily.

In case of any suspected systemic reactions related to patch application (including cutaneous reactions distant from the sites of patch application), the same safety precautions should be followed: the Viaskin® patch is removed immediately, the site of application wiped with a moist disposable tissue and a treatment can be given to treat the reaction: antihistamines or topical corticosteroids with additional oral corticosteroids or similar anti-allergic drugs, as deemed necessary by the Investigator. The next Viaskin® patch should be applied the next day on the next zone. As a consequence, the daily duration of patch application should be adjusted/reduced as necessary, and subjects may need more time than initially defined before they can apply the Viaskin® patch for the full 24 hours daily.

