## 9.9 Data and Safety Monitoring Board

A DSMB composed of experts in food allergy and in the methodology of clinical studies will be established in due time for the first data review. This DSMB will be independent of the Sponsor and will review safety data from the study at specified intervals during the study and on an ad hoc basis as deemed necessary by the DSMB Chair person or when conveyed by the Sponsor. A specific DSMB meeting will be held when the first 15 subjects 4 to 5 years of age have been randomized and treated for at least 4 weeks (that is, have completed the Month 1 visit). This is to assess very early in the study that safety of Viaskin® Peanut in these younger patients is acceptable.

The DSMB members will review blinded data, but may have access to unblinded data as deemed necessary during the closed review meetings. During these review meetings, the DSMB will assess whether the nature, frequency, and severity of the AEs associated with the study treatment warrant any recommendations or corrective actions in the best interest of the subjects.

The roles, responsibilities, constitution, and operations of the DSMB will be described in the DSMB Charter, which will be reviewed and signed by each member before the first subject is randomized and treated.

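### Leaflet stopping rule 6b (Protocol 5.2.2) makes withdrawal after severe patch-related anaphylaxis depend on a review that Protocol 4.3.1 does not require and that is not defined for one child

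*Protocol*

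**What the plan says.** Protocol 4.3.1 lists the events for which withdrawal from study treatment is mandatory. The anaphylaxis entry begins "Severe anaphylaxis (or stage 3 anaphylaxis", points to the staging in Appendix 5, and limits the event to one related to patch application. It asks for no confirmation.

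Protocol 5.2.2 sets out the minimum content of a safety leaflet given to each subject. Item 6 gives the subject stopping rules and says that subjects who meet them are withdrawn. Item 6b names severe anaphylaxis related to "patch application confirmed by an expedited safety review".

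One other place uses the term expedited safety review. Protocol 4.3.2 opens with "Study enrollment will be suspended pending an expedited safety review by the independent DSMB if any of the following occur". The anaphylaxis trigger there begins "More than one case of severe anaphylaxis (or stage 3 anaphylaxis". Protocol 9.9 also lets the DSMB review safety data "on an ad hoc basis as deemed necessary by the DSMB Chair person or when conveyed by the Sponsor".

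Protocol 5.2.1 covers day-to-day adjustment of the patch. For systemic reactions it starts "In case of any suspected systemic reactions related to patch application (including cutaneous reactions distant from the sites of patch application", has the patch removed, and says that the next "patch should be applied the next day on the next zone. As a consequence, the daily duration of patch application should be adjusted/reduced as necessary".

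**The concern.** Two stated rules for the same life-threatening event differ on when a child stops treatment, and the looser one is in the text meant for families. Stage 3 in Appendix 5 covers cyanosis or low oxygen saturation, hypotension, confusion, collapse, loss of consciousness and incontinence, here in children from age 4.

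Under 4.3.1 the first such event ends treatment. Under 6b a family, or a site working from the leaflet, could take withdrawal to depend on a review. The protocol does not say who carries out that review for one child, how quickly, or whether daily patches continue meanwhile.

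The stake is patient safety: a possible delay in stopping dosing. There is also a small analysis link. SAP Appendix 1 treats failure to withdraw a subject who met withdrawal criteria as a major deviation that can remove the subject from the PP population. The criterion should therefore have one reading.

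**Working it through.** The point rests on comparing text. There is no plan figure to reproduce.

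**Step 1. Item 6 against 4.3.1.**

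| Event | Protocol 4.3.1 | Protocol 5.2.2 item 6 |
|---|---|---|
| Severe rash or dermatitis | Uncontrolled by adequate treatment, topical steroids included, and despite several treatment interruptions | 6a: at patch sites, uncontrolled by topical steroids; interruptions not mentioned |
| Severe patch-related anaphylaxis | One event, no condition | 6b: one event plus confirmation by an expedited review |
| Epinephrine | More than 1 injection for a patch-related event outside the food challenge | 6c: the same in substance, no confirmation |
| Pregnancy | Listed | Not listed |

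Only 6b adds a confirmation step. It is not the only departure, since 6a also differs.

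**Step 2. Which review could 6b mean?** The review in 4.3.2 is done by the DSMB. It has three triggers: a death related to patch dosing, more than one case of severe anaphylaxis, or more than 3 subjects each needing more than 1 epinephrine injection. Its three outcomes are that accrual continues unchanged, continues with modifications, or is discontinued. None is a finding about one child's event. Ad hoc review under 9.9 could take up a first case, but nothing requires it to.

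**Step 3. Count the cases.** Section 4.3.1 acts on 1 case. The anaphylaxis trigger in 4.3.2 needs more than 1, so at least 2. If 6b means the 4.3.2 review (an inference, since 6b names neither the DSMB nor that section), a first non-fatal case meets 4.3.1 without meeting the anaphylaxis trigger.

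**Step 4. The next-day patch instruction.** Section 5.2.1 sets no severity limit on systemic reactions, does not refer to 4.3.1 and makes no exception for its events. Its listed treatments are "antihistamines or topical corticosteroids with additional oral corticosteroids or similar anti-allergic drugs, as deemed necessary by the Investigator". Epinephrine is not named, which suggests that milder reactions were in mind.

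**Step 5. How often might this arise?** The documents give no rate for stage 3 anaphylaxis caused by the patch.

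- VIPES (Protocol 1.1.1.2.3): 14 placebo responders were 25.0%, so placebo n = 14 / 0.25 = 56 and active n = 221 − 56 = 165, over three doses and all ages. With no patch-related serious adverse event, the one-sided 95% upper bound is 1 − 0.05^(1/165) = 1.8%. This bounds any such event; it is not an expected rate of stage 3 anaphylaxis.
- CoFAR6 (Protocol Table 2, data to 25 May 2014): 1,028 + 2,751 = 3,779 reported doses, none leading to epinephrine. The split by arm is not shown.
- ARACHILD (Protocol 1.1.1.2.2, 100 µg): one anaphylactic reaction after a meal was judged possibly related to study drug, stage not stated. Relatedness can be unclear, and that is where a confirmation clause could cause delay.

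**The case against.** The best answer is that 4.3.1 is the governing rule and is unambiguous. Section 5.2.2 only lists what a leaflet will contain at a minimum, and families do not decide withdrawal. Other safeguards apply: the leaflet carries an Anaphylaxis Emergency Action Plan, families are told to call the site about unexpected reactions, serious events are reported within 24 hours of the site learning of them, and the investigator may withdraw a child at discretion. All of this stands and keeps the practical risk low. It does not make 6b correct.

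Item 6 also reads like a loose summary of 4.3.1. That is fair, and it rules out treating the mismatch as peculiar to anaphylaxis. It also argues for aligning the whole item.

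Three stronger readings are tempting, and the documents do not support them:

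- *That 6b can never be met for a first case.* This assumes that its review is the one in 4.3.2. The word confirmed may refer only to severity or relatedness, ad hoc DSMB review is allowed, and 9.9 lets the DSMB recommend corrective action in subjects' interest, not only on accrual.
- *That the plan directs a new patch the day after stage 3 anaphylaxis.* Section 5.2.1 says should where 4.3.1 says must, and its treatment list points to milder reactions. The missing exception is a drafting gap.
- *That efficacy results are at risk.* Nothing here materially changes the primary ITT analysis.

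**Conclusion.** Item 6b is wrong as written. It attaches to a mandatory withdrawal event a condition that 4.3.1 does not have, and the protocol defines no review of one child that could satisfy it. The difference bites on the first case, where 4.3.1 already requires withdrawal.

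The size is small: low practical risk, an event that should be rare, and no material effect on the primary analysis. It is still worth correcting, because the rule concerns a life-threatening reaction and the correction costs almost nothing.

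The conclusion assumes that the leaflet follows the 5.2.2 outline. Neither the leaflet nor the action plan is in the documents, and either may say more.

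**What to change.** Delete the last six words of "patch application confirmed by an expedited safety review" from item 6b, and align item 6, including 6a, with 4.3.1.

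Optionally, add to 5.2.1 and the leaflet: *If a 4.3.1 withdrawal criterion is met, no further patch is applied and the subject is withdrawn from study treatment; if one is suspected, no further patch is applied until the Investigator has determined whether it is met.* The two cases need to stay separate: a single hold-and-assess line would suggest that a child who meets a criterion might resume. For the same reason, the vesicle procedure in 6.2.1.3.5 is not a suitable model, since it is built around restarting the patch.

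The cost is a clarification or minor amendment and a leaflet revision, with no change to visits, sample size or analysis. The downside of the optional line is a few missed patch days when a suspected event proves not to meet 4.3.1. Assuming a hold of 1 to 3 days, that is 1/365 = 0.3% to 3/365 = 0.8% of the year, against 365 − 0.80 × 365 = 73 days of slack under the 80% compliance threshold.
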